2.2.1 Subgroup of interest

Efficacy

The primary endpoint (DFS) and key secondary endpoint (OS) will be summarized by the following subgroups to examine homogeneity of treatment effect, provided that the corresponding primary efficacy analysis and key secondary efficacy analysis based on the FAS are statistically significant respectively:

- AJCC/UICC v. 8 stage (IIA vs. IIB vs. IIIA vs. IIIB with T>5cm, N2 disease) based on randomization data from IRT
- AJCC/UICC v. 8 stage (IIA vs. IIB vs. IIIA vs. IIIB with T>5cm, N2 disease) based on eCRF data
- Histology (squamous vs. non-squamous) based on randomization data from IRT

- Histology (squamous vs. non-squamous) based on eCRF data
- Region (Western Europe and North America vs. eastern Asia vs. Rest of the world (RoW)) based on randomization data from IRT
- Sex (Male vs. Female)
- Race (White vs. Black vs. Asian vs. Others (includes “Native Hawaiian or Other Pacific Islander” and “American Indian or Alaska Native”))
- Age category (<50 years vs. (≥50 years and <65 years) vs. (≥65 years and <75 years) vs. ≥75 years)
- ECOG PS status (0 vs. ≥ 1)
- Smoking history (never vs. former smoker vs. current smoker)

█ [REDACTED]

█ [REDACTED]

- EGFR mutant status (mutant vs. non-mutant) based on *local* testing during screening
- Prior chemotherapy (yes vs. no) in subjects with stage IIA and N0 disease based on eCRF data
- Prior radiotherapy (yes vs. no) in subjects with N2 disease based on eCRF data
- PD-L1 categories (<1%, ≥ 1 %, < 50%, ≥ 50%, ≥ 1 % and < 49%)
- CD8 categories by median or quartile (including its complements)

No formal statistical test of hypotheses will be performed for the subgroups. Kaplan-Meier method will be used for summarizing medians and their corresponding 95% C.I. of DFS or OS. Hazard ratio (HR) for the treatment effect and its 95% confidence intervals will be summarized based on Cox regression model stratified by randomization stratification factors. The objective of the efficacy subgroup analysis is to demonstrate homogeneity of treatment effect in the above subgroups.

Safety

Key safety analyses, including AEs and AESIs, will be repeated on safety set in the following subgroups:

- Sex (Male vs. Female)
- Race (White vs. Black vs. Asian vs. Others (includes “Native Hawaiian or Other Pacific Islander” and “American Indian or Alaska Native”))
- Age category (<50 years vs. (≥50 years and <65 years) vs. (≥65 years and <75 years) vs. ≥75 years)
- ECOG PS status (0 vs. ≥ 1)
- Smoking history (former or never smoker vs. current smoker)
- Prior chemotherapy and no prior radiotherapy vs. no prior chemotherapy and no prior radiotherapy

- Prior radiotherapy (yes vs. no) in subjects with N2 disease based on eCRF data
- BMI $\geq 35\text{kg/m}^2$ at baseline (yes vs. no)
- PD-L1 categories (<1%, $\geq 1\%$, < 50%, $\geq 50\%$, $\geq 1\%$ and < 49%)
- CD8 categories by median or quartile (including its complements)

The objective for carrying out these subgroup analyses is to identify potential safety issues that may be limited to a subgroup of subjects, or safety issues that are more commonly observed in a subgroup of subjects.

The following safety summaries will be performed by subgroup:

- AEs, regardless of study treatment, by primary system organ class and preferred term
- AEs with suspected relationship to study treatment by primary system organ class and preferred term
- Adverse Event of Special Interest, irrespective of causality, by grouping, preferred term, maximum grade, and treatment

Country-specific subgroup analyses

Key efficacy and safety outputs, including baseline characteristics, PK and immunogenicity, will be repeated for Japanese subjects and Non-Japanese subgroup respectively.

2.3 Subject disposition, demographics and other baseline characteristics

The Full Analysis Set (FAS) will be used for all baseline and demographic summaries and listings unless otherwise specified. Summaries will be reported by treatment arm and for all subjects. In addition, listings will be reported by treatment arm to assess baseline comparability. No inferential statistics will be provided.

Basic demographic and background data

All demographic and baseline disease characteristics data will be summarized and listed by treatment. Categorical data (e.g. gender, age groups: <50 years vs. (≥ 50 years and <65 years) vs. (≥ 65 years and < 75 years) vs. ≥ 75 years, race, WHO performance status, and smoking history), PD-L1 categories (<1%, $\geq 1\%$, < 50%, $\geq 50\%$, $\geq 1\%$ and < 49%) and CD8 categories by median and quartile (including its complements) will be summarized by frequency counts and percentages; the number and percentage of subjects with missing data will be provided. Continuous data (e.g. age, weight, height, and body mass index (BMI)) will be summarized by descriptive statistics (e.g. N, mean, median, standard deviation, percentiles, minimum, and maximum). BMI (kg/m^2) will be calculated using weight and height at baseline.

In light of COVID-19 pandemic impacting the study during the enrollment phase, summary of demographic and baseline characteristics will be generated by groups of subjects who are enrolled in different pandemic phases to have an understanding of whether there is a shift in subject population characteristics. The pandemic phase will be divided into two phases: pre-pandemic period and pandemic period. [Table 2-4](#) specifies COVID-19 start and end dates by region/country to determine the pandemic phase.

Table 2-4 COVID-19 start and end dates by region/country

Region/Country	Start Date	End Date
China	01Jan2020	Not defined yet
South Korea	20Feb2020	Not defined yet
Japan	21Feb2020	Not defined yet
Italy	23Feb2020	Not defined yet
Rest of the world	01Mar2020	Not defined yet

Baseline stratification factors

The number (%) of subjects in each randomization stratum based on data obtained from the IRT system will be summarized overall and by treatment for the FAS. Discordances between the stratum recorded in IRT at the time of randomization and the actual stratum recorded in the clinical database through the data collected on eCRF will be cross-tabulated and listed.

Diagnosis and extent of cancer

Summary statistics will be tabulated for diagnosis and extent of cancer. This analysis will include the following: primary site of cancer, details of tumor histology/cytology, and TNM pathological staging after resection.

Medical history

Medical history and current medical conditions at screening, including cancer-related conditions and symptoms entered on (e) CRF, will be summarized and listed by primary system organ class (SOC), preferred term (PT), and treatment. They will be coded using the Medical Dictionary for Regulatory Activities (MedDRA) terminology.

Other

All data collected at baseline, including source of subject referral and other informed consents than main study informed consent, will be listed.

2.3.1 Subject disposition

All screened and randomized subjects will be summarized by country and center. The number (%) of randomized subjects will be presented overall and by treatment. The number (%) of screened subjects and not-randomized subjects, along with the reasons of screening failure, will be displayed. The number (%) of randomized subjects who are still on-treatment, who discontinued the treatment or study, along with the reasons for discontinuation, will be presented overall and by treatment.

The following summaries will be provided (with % based on the total number of FAS subjects):

- Number (%) of subjects who were randomized (based on data from IRT system)
- Number (%) of subjects who were randomized but not treated (based on 'DAR' eCRF page not completed for study treatment)
- Primary reason for not being treated (based on "Treatment disposition" eCRF page)

- Number (%) of subjects who were treated (based on ‘DAR’ eCRF pages of study treatment completed with non-zero dose administered)
- Number (%) of subjects who are still on-treatment (based on the ‘Treatment disposition’ page not completed);
- Number (%) of subjects who discontinued the study treatment (based on the ‘Treatment disposition’ page)
- Primary reason for treatment discontinuation (based on the ‘Treatment disposition’ page)
- Number (%) of subjects who discontinued study (based on the ‘Study disposition’ page);
- Reasons for study discontinuation (based on ‘Study disposition’ page)

2.3.2 Protocol deviations

Protocol deviations, including COVID-19 pandemic related and not related, will be summarized in total by treatment. In addition to the pre-defined standard protocol deviation terms, the following protocol deviations related to COVID-19 in line with “FDA Guidance on Conduct of Clinical Trials of Medical Products during COVID-19 Public Health Emergency” (March 2020) and “Guidance on the management of clinical trials during the COVID-19 (coronavirus) pandemic” (April 2020) from EMA will be summarized:

- Missing visits
- Changes in procedures and assessments
- Planned visits not done at sites
- Changes in drug supply method
- Treatment not given
- Subject discontinuation due to COVID-19 situation
- Dose interruption greater than 84 days

The relationship of protocol deviation to COVID-19 will also be summarized using the following descriptions:

- COVID-19 Health Status: (i.e. subject’s COVID-19 infection led to this PD)
- COVID-19 *Site issue: (e.g. site closed, personnel not available)
- COVID-19 Lockdown: (e.g. site is active but subject not allowed to come)
- COVID-19 Subject/Subject concern: (e.g. site is active, subject/subject could come but refused to come / do assessment)
- COVID-19 Drug supply issue (e.g. drug was delivered to home)
- COVID-19 Other: (e.g. situation not already covered by the information above)

* For deviation with multiple relationships, ‘Site Issue’ was reported as the primary relationship to COVID-19 if another relationship was also applicable.

In addition, COVID-19 related outcomes (e.g., COVID-19 AEs, treatment discontinuation and study discontinuation due to COVID-19, death due to COVID-19) will be descriptively summarized by country, site, and treatment.

All protocol deviations will be listed.

2.3.3 Analysis sets

The number (%) of subjects in each analysis set will be summarized by treatment and randomization stratum.

2.4 Treatments (study treatment, rescue medication, concomitant therapies, compliance)

2.4.1 Study treatment / compliance

Duration of exposure, actual cumulative dose, dose intensity (DI), and relative dose intensity (RDI) will be summarized by treatment. Duration of exposure will be categorized into time intervals; frequency counts and percentages will be presented for the number (%) of subjects in each interval. The number (%) of subjects who have dose interruptions, along with interruption reasons, will be summarized by treatment. No dose modification is allowed as per study protocol.

Subject level listings of all doses administered on-treatment, along with dose interruption reasons, will be produced.

The safety set will be used for all summaries and listings of study treatment.

Duration of exposure to study treatment

Last date of exposure and duration of exposure are defined as below:

- Last date of exposure to study treatment = last dosing date of study treatment + 20 days (If the subject died or was lost to follow-up before the derived last date of exposure, the last date of exposure to study treatment is the date of death or the date of last contact before lost to follow-up, respectively. If the derived last date of exposure goes beyond the data cutoff date, it should be truncated to the date of data cutoff.)
- Duration of exposure to study treatment (days):
last date of exposure to study treatment – first dosing date of study treatment + 1 (periods of interruption are not excluded)

Summary of duration of exposure of study treatment in months will include categorical summaries and continuous summaries (i.e. mean, standard deviation, etc.).

Cumulative dose

Cumulative dose of a study treatment is defined as the total dose given during the study treatment exposure.

The **planned cumulative dose** for a study treatment refers to the total planned dose per the protocol up to the last date of study treatment.

- Cumulative planned dose for a study treatment:
planned dose per cycle as per protocol * number of complete cycles the subject should have been over the duration of exposure
- Number of complete cycles: (last dosing date of study treatment – first dosing date of study treatment + 21)/21
- Planned dose per cycle as per protocol: 200 mg/cycle

The **actual cumulative dose** refers to the total actual dose administered, over the duration for which the subject is on the study treatment as documented in the Dose Administration eCRF.

2.4.2 Prior, concomitant and post therapies

Prior anti-cancer therapy

The number and percentage of subjects, who received prior anti-neoplastic medications, radiotherapies, or surgeries, will be summarized by treatment. Prior anti-neoplastic medications will also be summarized by therapy type, setting, lowest ATC class, preferred term, and treatment. Summaries will include total number of regimens. For radiotherapies, time since last radiotherapy, locations, and setting of last therapy will be summarized by treatment. For prior surgeries, time since last surgery, procedure, and residual disease of last therapy will be summarized by treatment. In addition, the summaries for prior antineoplastic medications and radiotherapies will be repeated by AJCC/UICC v.

8 stage (including Stage IIA, T2b, N0 T (>4 - 5cm) vs. IIB (T1abc-2ab) vs. IIB T3 >5cm & ≤7cm, N0 vs. IIIA T3 or T4 Tis>5 cm vs. IIIA T≤5cm vs. IIIB T>5cm).

Separate listings will be produced for prior anti-neoplastic medications, radiotherapies, and surgeries.

Anti-neoplastic medications will be coded using the WHO Drug Dictionary (WHO-DD); anti-neoplastic surgery will be coded using MedDRA. The above analyses will be performed using the FAS.

Post treatment anti-cancer therapy

Anti-neoplastic therapies since discontinuation of study treatment will be summarized and listed by ATC class, preferred term, and treatment by means of frequency counts and percentages using FAS. First new Anti-neoplastic therapies related to NSCLC since discontinuation of study treatment will be summarized as well.

Concomitant medications

Concomitant therapies are defined as interventions (therapeutic treatment or procedure), other than the study treatment, administered to a subject in the study treatment period. They includes concomitant medications and therapies.

Concomitant medications will be coded using the World Health Organization (WHO) Drug Reference Listing (DRL) dictionary that employs the WHO Anatomical Therapeutic Chemical (ATC) classification system and summarized by lowest ATC class and preferred term using frequency counts and percentages. Summaries will include:

- Medications starting on or after the start of study treatment but no later than 130 days after last dose of study treatment and
- Medications starting prior to start of study treatment and continuing after the start of study treatment

All concomitant therapies will be listed. Any concomitant therapies starting and ending prior to the start of study treatment or starting more than 130 days after the last date of study treatment will be flagged. Surgical and medical procedures will be coded using MedDRA and summarized by SOC, preferred term, and treatment.

The safety set will be used for all tables and listings of concomitant medications and therapies.

2.5 Analysis of the primary objective

The primary objective is to compare the DFS in the canakinumab versus placebo arms as determined by local investigator assessment.

2.5.1 Primary estimand

The primary efficacy variable of the study is DFS, defined as the time from the date of randomization to the date of the first documented disease recurrence as assessed by local investigator radiologically or death due to any cause. Disease recurrence includes diagnoses of new primary lung malignancies. Clinical deterioration is not considered as a recurrence of disease. In case of non-conclusive radiological evidence, a biopsy should be performed to confirm recurrence. If a biopsy is not feasible, the subject will be followed up until recurrence can be confirmed as per protocol (radiologically conclusive and/or biopsy)”; radiological assessment date will be used as DFS event date. The primary

analysis will be based on FAS and will include all data observed up to the cut-off date. Censoring conventions are provided in [Section 2.5.3](#).

The scientific objective guiding the primary estimand is to estimate the treatment effect based on the primary endpoint of DFS for canakinumab compared to placebo, for the randomized subjects enrolled with inclusion/exclusion criteria, which were defined in the protocol, irrespective of any treatment discontinuation reasons, any new malignancy not related to lung cancer and had the post-treatment antineoplastic therapies for NSCLC not been administered. It is expected that new therapies such as PD-L1s for adjuvant NSCLC may be approved during the conduct of this trial. In case placebo subjects in this study were to switch to these new approved therapies prior to disease recurrence, it can have a potential impact on the treatment effect in the placebo arm. Hence, the primary estimand uses a hypothetical strategy to assess the treatment effect based on DFS had the post-treatment antineoplastic therapies for NSCLC not been administered. Additional intercurrent events such as discontinuation of study treatment, appearance of new primary malignancy not related to lung, post-treatment antineoplastic therapies not related to lung, and intercurrent events due to COVID-19 pandemic are expected in both treatment arms. Hence, the primary estimand of interest will be to assess the treatment effect based on DFS, irrespective of these intercurrent events.

The primary estimand is described by the following five attributes:

1. The **target population** includes all randomized subjects (FAS).
2. The **primary variable** is DFS defined as the time from the date of randomization to the date of the first documented disease recurrence, assessed by local investigator radiologically, or death due to any cause. Any new primary lung malignancy will be handled as disease recurrence.
3. The **treatment of interest** is the randomized treatment (canakinumab arm or placebo arm).
4. The remaining intercurrent events describe how events that may occur after randomization are considered when assessing the treatment effect.
 - Discontinuation of study treatment: DFS will take into account all DFS assessments, irrespective of the study treatment discontinuation reasons (treatment policy)
 - Initiation of post-treatment anti-neoplastic therapies for NSCLC: DFS will be censored at the last adequate tumor assessment prior to the initiation of post-treatment antineoplastic therapy (hypothetical strategy)
 - New primary malignancy not related to Lung cancer: DFS will take into account all DFS assessments, irrespective of the occurrence of any new malignancy not related to lung cancer (treatment policy)
 - Initiation of post-treatment anti-neoplastic therapies for malignancies not related to lung cancer: DFS will take into account all DFS assessments, irrespective of initiation of any post-treatment antineoplastic therapies for new malignancy not related to lung cancer (treatment policy)
 - Any unforeseen intercurrent events due to COVID-19 pandemic will be handled by treatment policy strategy
5. The **summary measure** is the hazard ratio (HR) for DFS between two treatment arms. It will be estimated using Cox proportional hazard model stratified by randomization stratification factors.

2.5.2 Statistical hypothesis, model, and method of analysis

Assumed proportional hazards model for DFS, the following statistical hypotheses will be tested to address the primary efficacy objective:

H_{01} (null hypotheses): $\Theta_1 \geq 0$ vs. H_{a1} (alternative hypotheses): $\Theta_1 < 0$

Where Θ_1 is the log hazard ratio of DFS in the canakinumab (investigational) vs. placebo (control).

The primary efficacy analysis to test this hypothesis and compare the two arms will involve a stratified log-rank test at an overall one-sided 2.5% level of significance. The stratification will be based on the following randomization stratification factors: AJCC/UICC v8 stage IIA versus IIB versus IIIA versus IIIB with T>5cm N2 disease; Histology: squamous versus non-squamous; and Region: Western Europe and North America vs. eastern Asia vs. Rest of the world (RoW). A group sequential design is employed for the primary efficacy variable DFS. One interim analysis, along with a final analysis, is planned, using a Lan-DeMets (O'Brien-Fleming) α -spending function for efficacy and a non-binding user-defined β -spending function (gamma function with $\gamma=-3$) for futility. There is only futility assessed at the IA.

The DFS distribution will be estimated using the Kaplan-Meier method, and Kaplan-Meier curves will be plotted for each arm. The DFS Kaplan-Meier estimate along with 95% confidence intervals will be presented by year for each arm. The hazard ratio for DFS will be calculated, along with its 95% confidence interval, from a stratified Cox model using the same stratification factors as those for the log-rank test.

2.5.3 Handling of missing values/censoring/discontinuations

For subjects who received any subsequent anti-neoplastic therapy for NSCLC, the following rules will apply:

- If new NSCLC anti-neoplastic therapy is started without evidence of documented disease recurrence, then DFS will be censored at the date of last tumor assessment before the date of initiation of anti-cancer therapy
- If a subject does not have any tumor assessment before the date of initiation of new anti-neoplastic therapy for NSCLC, DFS will be censored at the date of randomization.

Clinical review will be performed to determine if anti-neoplastic therapy is NSCLC related in case of multiple malignancies.

Any new primary malignancies *not* related to lung or clinical deterioration will not be considered as a disease recurrence.

Event/censoring dates for the primary estimand will be determined by [Table 2-5](#):

Table 2-5 Outcome and event/censoring dates for primary DFS analysis

Situation	Date	Outcome
Evidence of unresected NSCLC or distant metastatic NSCLC disease on screening evaluation	Date of randomization	Censored
Death before any tumor assessment	Date of death	Event

Situation	Date	Outcome
Recurrence or death documented between scheduled visits	Date of tumor assessment (or death)	Event
No recurrence (or death)	Date of last adequate tumor assessment	Censored
New antineoplastic therapy (including surgery) for NSCLC given prior to recurrence or death	Date of last adequate assessment on or prior to starting new anti-cancer therapy	Censored
New antineoplastic therapy (including surgery) for NSCLC prior to any scheduled visit	Date of randomization	Censored
New primary lung malignancies	Date of tumor assessment	Event

The DFS censoring reasons are defined in the following way. If the date is the earliest of the following dates:

- Analysis cut-off date
- Date of consent withdrawal
- Date of new NSCLC antineoplastic therapy
- Date of lost to follow-up

Then the DFS censoring reason will be:

- Ongoing without event
- Withdrew consent
- New NSCLC antineoplastic therapy
- Lost to follow-up

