MACE	Major adverse cardiovascular events
MCV	Mean Corpuscular Volume
mg	Miligram
MI	Myocardial infarction
MKD	Mevalonate Kinase Deficiency
mL	Mililiter
MRI	Magnetic Resonance Imaging
NSCLC	Non-small cell lung cancer

Novartis Amended Protocol Version 03 (Clean) Confidential

OS	overall survival
PD	Pharmacodynamics
PK	Pharmacokinetics
PHI	Protected Health Information
PPS	Per protocol set
PRO	Patient-Reported Outcome
PT	Prothrombin Time
PTS	Post treatment surveillance
q3w	Every 3 weeks
QFT-PLUS	QuantiFERON®-TB Gold Plus assay
QLQ	Quality of Life Questionnaire
QoL	Quality of Life
R0	Completely resected
RDE	Recommended dose for expansion
REB	Research Ethics Board
RNA	Ribonucleic Acid
R Value	ALT/ALP in x ULN
SAE	Serious Adverse Event
SAP	Statistical Analysis Plan
S.C.	Subcutaneous
SJIA	Systemic Juvenile Idiopathic Arthritis
SS	Survival Status
SST	Serum Seperating Tube
SUSAR	Suspected Unexpected Serious Adverse Reaction
T1D	Type 1 Diabetes
Т3	Triiodothyronine
T4	Thyroxine
TBIL	Total bilirubin
TNF	Tumor Necrosis Factor
TRAPS	Tumor Necrosis Factor Receptor Associated Periodic Syndrome
TSH	Thyroid-Stimulating Hormone
UICC	Union for International Cancer Control
ULN	Upper limit of normal
VES	Visit Evaluation Schedule

Glossary of terms

Assessment	A procedure used to generate data required by the study
Biologic Samples	A biological specimen including, for example, blood (plasma, serum), saliva, tissue, urine, stool, etc. taken from a study subject or study subject
Control drug	A study treatment used as a comparator to reduce assessment bias, preserve blinding of investigational drug, assess internal study validity, and/or evaluate comparative effects of the investigational drug
Cohort	A group of individuals who share a common exposure, experience or characteristic, or a group of individuals followed-up or traced over time
Cycles	Number and timing or recommended repetitions of therapy are usually expressed as number of days (e.g.: q28 days)
Discontinuation from study	Point/time when the subject permanently stops receiving the study treatment and further protocol required assessments or follow-up, for any reason. No specific request is made to stop the use of their samples or data.

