- Non-compliance, as defined by missing any single dose greater than 42 days from the intended day of the next scheduled dose.
- Initiation of a new antineoplastic therapy

Subjects who become pregnant during the trial must be withdrawn (Section 8.4). Subjects who become pregnant must cease all tumor assessments regardless of whether or not they developed recurrence.

The appropriate personnel from the site and Novartis will assess whether study treatment should be discontinued for any subject whose treatment code has been broken inadvertently for any reason.

Discontinuation from study is when the subject permanently stops receiving the study treatment, and further protocol-required assessments or follow-up, for any reason.

If the subject agrees, a final evaluation at the time of the subject's study discontinuation should be made as detailed in the assessment table (refer to Table 7-1).

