10.4.4 Supportive and Sensitivity analyses

As sensitivity analyses performed in the FAS, the hazard ratio and 95% confidence interval for DFS will be obtained from:

- an unstratified and covariate unadjusted Cox model.
- stratified Cox model using a modified definition of DFS event with the inclusion of the start of anti-neoplastic therapy as a DFS event in addition to NSCLC disease recurrence defined for primary analysis.
- stratified Cox model without censoring NSCLC related anti-neoplastic therapy
- stratified Cox model with censoring two or more missing assessments
- stratified Cox model with censoring subjects when discontinuing treatment or death due to COVID-19, or receiving COVID-19 medications
- a stratified and covariate adjusted Cox model including covariates such as gender, age and smoking history.

The final list of covariates to be included in the model will be provided in the SAP.

If the primary analysis is statistically significant, subgroup analyses to assess the homogeneity of the treatment effect across demographic and baseline disease characteristics will be performed including AJCC/UICC v.8 stage, histology and region. Other subgroups to be considered will be defined in the SAP.

The number of subjects censored and reasons for censoring for DFS will be summarized by treatment group using descriptive statistics.

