5.6 Missing tumor assessments

The term ‘missing adequate tumor assessment’ is defined as a tumor assessment not done. For the sake of simplicity, a ‘tumor assessment’ will be referred to as an ‘assessment’ and a ‘missing adequate tumor assessment’ will be referred to as a ‘missing assessment’.

The presence and the number of missing assessments affects DFS censoring and event date.

An exact rule to determine whether there is no, one or two missing assessments is therefore needed. This rule is based:

- on the duration between LATA date and the event date
- on the duration between LATA date and the cut-off date

In this study, the protocol defined schedule of assessments is

- every 12 weeks during the first year (i.e. at weeks 12, 24, 36 and 48),
- every 26 weeks through year 2 and year 3 (i.e. at weeks 74, 100, 126 and 152),
- every 52 weeks through year 4 and year 5 (i.e. at weeks 204 and 256).

The scheduled date of assessments (in weeks from randomization), protocol specified windows for assessment, and the thresholds for LARA to belong to a visit can be found in [Table 5-3](#).

Table 5-3 Schedule for assessments, time windows and D1/D2 (weeks)

assessment schedule		Scheduled date – one week*	Schedule date (weeks from randomization)	Scheduled date + one week*	Threshold (weeks)**	Boundary of assessment*** (start, end]	D1/D2****
Every 12 weeks for the first year	1 st (C5D1)	11	12	13	18	(0,18]	14/26
	2 nd (C9D1)	23	24	25	30	(18,30]	14/26
	3 rd (C13D1)	35	36	37	42	(30,42]	14/40
	4 th (C17D1)	47	48	49	61	(42,61]	28/54
Every 26 weeks for the second and third year	5 th	73	74	75	87	(61,87]	28/54
	6 th	99	100	101	113	(87,113]	28/54
	7 th	125	126	127	139	(113,139]	28/80
	8 th	151	152	153	178	(139,178]	54/106
Every 52 weeks for the four and fifth year	9 th	203	204	205	230	(178,230]	54/106
	10 th	255	256	257	282	(230, 282]	54/106

* These start and end study weeks are used to determine if a visit is on schedule. For example, a visit between study week 23 and study week 25 is considered the 2nd ‘on schedule’ assessment.

** The threshold correspond to the mid-point between current and next visit and to the upper limit for LARA to be matched to a certain scheduled assessment e.g. if LARA is at week 45, this is after the threshold for 3rd recurrence assessment (C13D1) and before that for the 4th recurrence assessment, so the matching schedule assessment is the 4th recurrence assessment (C17D1).

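### The SAP's DFS censoring-reason rule has no category for subjects who leave the study or stop scans without withdrawing consent or being lost, or for disease found at screening, so it reports them as ongoing

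*SAP*

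**What the plan says.** SAP 2.5.3 pairs four dates with four reasons and lets the earliest date decide: "The DFS censoring reasons are defined in the following way. If the date is the earliest of the following dates". The cut-off gives "Ongoing without event"; the other three give consent withdrawn, new NSCLC therapy and lost to follow-up. For a subject without recurrence or death, Table 2-5 in the same section puts the censoring date elsewhere, at the "Date of last adequate tumor assessment". Table 2-5 also censors at randomization anyone with unresected or distant metastatic NSCLC on the screening evaluation, but no reason is listed for them.

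The protocol has a status that the four dates do not cover. Its Glossary defines discontinuation from study as the "Point/time when the subject permanently stops receiving the study treatment and further protocol required assessments or follow-up, for any reason", and adds: "No specific request is made to stop the use of their samples or data". Withdrawal of consent (Protocol 7.1.5) is narrower, because the subject must also refuse further collection of personal data. Loss to follow-up (Protocol 7.1.7) is for subjects who go silent without saying that they intend to leave.

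The summary is a planned output. Protocol 10.4.4 states: "The number of subjects censored and reasons for censoring for DFS will be summarized by treatment group using descriptive statistics".

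**The concern.** The label and the censoring date come from different sources, and nothing compares them. A subject whose last scan was years before the cut-off gets the same label as one scanned last month, provided none of the other three dates is recorded.

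A table of censoring reasons by arm is a natural place to ask whether censoring of the primary endpoint is administrative or could be informative, and whether it differs between arms. If people who left assessment are counted as still under observation, the administrative category is too large in each arm by an unknown amount, and an imbalance in early departure could go unseen in that table.

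The SAP is stricter for its other survival endpoints. For OS (2.6.3) and lung cancer specific survival (2.7.1), a gap of more than 14 weeks between last contact and cut-off is labelled lost to follow-up. DFS, which depends on scheduled imaging, has no equivalent check.

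**Working it through.** **1. Apply the rule to example subjects.** Take a cut-off at week 182 (an assumption, about 42 months).

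| Subject | Listed dates present | Reason assigned | What happened |
|---|---|---|---|
| Scans up to date | cut-off | ongoing | correct |
| Scan at week 24, then leaves the study; consent not withdrawn, not lost | cut-off | ongoing | 182 − 24 = 158 weeks unobserved |
| Pregnancy, last scan at week 36 | cut-off | ongoing | 182 − 36 = 146 weeks unobserved |
| Disease found at screening | cut-off | ongoing | censored at randomization |
| Consent withdrawn at week 30 | week 30, cut-off | consent withdrawn | correct |
| Lost at week 30 | week 30, cut-off | lost to follow-up | correct |

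The pregnancy row follows Protocol 7.1.4: "Subjects who become pregnant must cease all tumor assessments regardless of whether or not they developed recurrence". Protocol 6.4.2.1 gives another route, since a live or attenuated vaccine during the study means discontinuation from the trial.

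**2. Does another part of the SAP repair the label?** Appendix 5.6 names the relevant gap as a basis for its rule ("on the duration between LATA date and the cut-off date"). Its counting rule, however, is written only for an event that falls after the last assessment plus D1 or D2. The sensitivity analysis for two or more missing assessments (SAP 2.5.4.1) changes no reason label.

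**3. Bound on the number affected.** Inputs from Protocol 10.8: 1500 subjects randomized 1:1, 30 months of accrual at 50 per month, analysis at month 42, placebo median DFS 48 months, hazard ratio 0.716, 5% yearly dropout. Even accrual makes follow-up uniform on 12 to 42 months.

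- Event hazards per month: placebo ln 2 / 48 = 0.01444; canakinumab 0.716 × 0.01444 = 0.01034.
- Dropout hazard: d = −ln(0.95) / 12 = 0.00427.
- With t = h + d, the mean probability that an event or dropout has occurred is q = 1 − [exp(−12t) − exp(−42t)] / (30t). This gives q = 0.389 for placebo and 0.321 for canakinumab.
- P(event) = q·h/t = 0.300 and 0.227. Expected events: 750 × (0.300 + 0.227) ≈ 395, against the planned 392, so the plan's figure is reproduced.
- P(dropout first) = q·d/t = 0.0888 and 0.0938. Expected dropouts: 750 × (0.0888 + 0.0938) ≈ 137. Reading 5% as a constant rate of 0.05/12 gives about 134.
- Subjects with neither: 1500 − 395 − 137 = 968.

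The 137 covers dropout for any cause. The documents do not say what share is neither lost nor a consent withdrawal, so the mislabelled number runs from 0 (share 0%) to about 137 (share 100%). Each 10 percentage points of that share moves about 14 subjects (0.10 × 137). At the upper end the ongoing category would be inflated by 137 / 968 ≈ 14%. Scaled to the 1382 randomized, the upper end is 137 × 1382 / 1500 ≈ 126, if follow-up were as planned. Disease-at-screening cases are extra, and the documents give no count.

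**The case against.** The strongest reply is that this is a descriptive label with cover elsewhere. SAP 2.3.1 reports study discontinuations and their reasons by treatment. SAP 2.7.2 reports, by arm, time from randomization to cut-off, time to event or censoring, and Kaplan-Meier follow-up for DFS, with the stated aim of describing maturity and quality of follow-up. This stands in part. A reader might infer that incomplete follow-up is hidden altogether, and it is not. What is missing is the link between those losses and DFS censoring.

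Protocol 7.1.4 also lets leavers be considered withdrawn if they say so or stop attending. That wording is permissive and concerns withdrawal from the study, whereas the SAP rule uses the date of consent withdrawal, so the gap remains.

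Other stronger readings are tempting but unsupported:

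- *A large share of dropouts is mislabelled.* The documents give no share, and Protocol 7.1.7 already treats silent non-attenders as lost.
- *New NSCLC therapy is the wrong reason when scans stopped long before it.* That label follows Table 2-5 and the hypothetical strategy of the primary estimand (SAP 2.5.1).
- *Disagreement with the disposition counts is itself an error.* SAP 2.3.1 counts every randomized subject who discontinued the study, including those with a DFS event, so the totals were not meant to match.
- *D1 in Appendix 5.6 is a ready-made test of being current.* It assumes a one-week window, while Protocol 7.2.1 allows 14 days in years 1 to 3 and 21 days in years 4 and 5. A subject scanned at week 22 (the week-24 visit, in window) may have the next scan as late as week 38. With a cut-off at week 37 the gap is 15 weeks, above D1 = 14, although the subject is on schedule.

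**Conclusion.** The rule in SAP 2.5.3 is wrong as written. It gives a false reason to subjects who discontinue the study or stop scans without withdrawing consent or being lost, and to those censored for disease at screening, unless another listed date applies. The by-arm summary of DFS censoring reasons then overstates administrative censoring.

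The size cannot be fixed from the documents. The bound of 0 to about 137 of 1500 rests on exponential event and dropout times, even accrual, and the plan's 5% yearly dropout. The SAP's document history notes slower enrollment than expected, so actual follow-up may differ. Disease-at-screening cases come on top.

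A reader might infer that the primary result is affected. It is not: the label enters neither the censoring date, the log-rank test nor the Cox model. This is a reporting defect in one summary of the primary endpoint, worth correcting because the correction is cheap.

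**What to change.** In SAP 2.5.3:

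1. Add three separate reasons: *Discontinued study*, *Adequate assessment no longer available* and *Disease at screening*. The first uses the study disposition page when the exit was neither consent withdrawal nor loss to follow-up. The third matches the first row of Table 2-5.
2. Reserve "Ongoing without event" for subjects whose last adequate assessment is current at cut-off, meaning that the gap does not exceed the scheduled interval plus the protocol-allowed windows at both ends. That is 12 + 2 + 2 = 16 weeks in year 1, 26 + 2 + 2 = 30 weeks for the 26-week intervals, 52 + 2 + 3 = 57 weeks from the week-152 to the week-204 scan, and 52 + 3 + 3 = 58 weeks after that. Do not use the D1 values of Appendix 5.6 (14, 28 and 54 weeks).
3. Leave the new NSCLC therapy reason as it is.
4. Report all reasons by arm.

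The cost is a few lines of SAP text and one derived variable, with no new data. The close-out SAP refers to a primary analysis report that already exists, so in practice this can be one corrected table or a footnote to it.
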